### 5.2.6. Subgroup Analysis

For each of the subgroups defined in Section 2.4, the proportion of subjects achieving IGA score of cleared (0) or minimal (1) and the proportion of PASI 90 responders at Week 16 by treatment group will be summarized. Differences in the proportion and the associated exact 95% confidence interval (CI) for the differences will be provided.

In addition, the proportion of subjects achieving IGA score of cleared (0) or minimal (1) and the proportion of PASI 90 responders at Week 16 by country and investigator site will be summarized.

### 5.3. Major Secondary Endpoints

The analyses for the major secondary endpoints will be performed in the order listed in Section 5.1.1.1.

The sections below outline the major secondary analyses to be performed, as well as the analysis methods and the data imputation rules.

#### 5.3.1. Definition

There are 2 major secondary endpoints in this study to be compared between the guselkumab 100 mg group and the placebo group:

- The proportion of subjects who achieve an IGA score of cleared (0) at Week 16.
- The proportion of subjects who achieve a PASI 100 response at Week 16.

#### 5.3.2. Analysis Methods

For the major secondary analyses, the Fisher's exact test will be used to compare the proportion of subjects responding to treatment. The differences in proportions with exact 95% confidence intervals will be presented. All statistical testing will be performed 2-sided ( $\alpha=0.05$ ).

#### 5.3.3. Data Handling

Data handling rules specified in Section 5.2.4 will be applied to the major secondary analyses.

#### 5.4. Other Efficacy Variable(s)

Other secondary efficacy endpoints include the endpoints related to

- PASI
- IGA

The analyses of other secondary efficacy analyses outlined in the following sections in general will be carried out for 2 periods

- Analyses through Week 20:
  - Analyses at key endpoints: Week 16
  - Over time summaries: Through Week 20
- Analyses through Week 40

##### 5.4.1. Definition

Refer to Section 5.1.2 for the definitions of the other efficacy endpoints described in the following section.

##### 5.4.2. Analysis Methods

Most of the other secondary efficacy analyses described in this section below will be based on the full analysis set. For subjects randomized to placebo, only subjects who crossed over to receive guselkumab 100 mg at Week 16 will be included in the efficacy summaries for the visits after Week 16. All statistical testing will be performed at the 2-sided 0.05 significance level. Nominal p-values will be presented.

##### 5.4.2.1. Analyses Related to IGA

- The proportion of subjects who achieve an IGA score of mild or better ( $\leq 2$ ) at Week 16 will be compared between the guselkumab 100 mg groups and the placebo group using Fisher's exact test. The difference in proportions with exact 95% confidence interval will be presented.
- The proportions of subjects achieve an IGA score of cleared (0); an IGA score of cleared (0) or minimal (1); and an IGA score of mild or better ( $\leq 2$ ) will be summarized over time through Week 20 and through Week 40 by treatment group. Line plots will be provided displaying the proportions and exact 95% CIs of subjects achieve an IGA score of cleared (0); and an IGA score of cleared (0) or minimal (1) through Week 20 and Week 40.
- The proportions of subjects achieving an IGA score of cleared (0); an IGA score of cleared (0) or minimal (1); and an IGA score of mild or better ( $\leq 2$ ) will also be summarized over time through Week 20 and through Week 40 by treatment group using observed data after applying treatment failure rules.

#### **5.4.2.2. Analyses Related to PASI**

- The proportion of subjects who achieve a PASI 75 response and a PASI 50 response at Week 16 will be compared between the guselkumab 100 mg groups and the placebo group using Fisher's exact test. The differences in proportions with exact 95% confidence intervals will be presented.
- The percent improvement from baseline in PASI score at Week 16 will be compared between the guselkumab 100 mg groups and the placebo group using Wilcoxon rank-sum test.
- The proportions of PASI 100 responders, PASI 90 responders, PASI 75 responders, and PASI 50 responders, and the percent improvement from baseline in PASI will be summarized over time through Week 20 and through Week 40 by treatment group. Line plots will be provided displaying proportions and exact 95% CIs of PASI 100 responders and PASI 90 responders through Week 20 and Week 40.
- The proportions of PASI 100 responders, PASI 90 responders, PASI 75 responders, and PASI 50 responders, and the percent improvement from baseline in PASI will be summarized over time through Week 20 and through Week 40 by treatment group using observed data after applying treatment failure rules.
- The proportion of subjects who achieve 100% improvement,  $\geq 90\%$ ,  $\geq 75\%$ , or  $\geq 50\%$  improvement from baseline in PASI component (induration, erythema, and scaling) and region component (head, trunk, upper extremities, and lower extremities) will be summarized at Week 16 by treatment group.

#### **5.4.3. Data Handling**

Data handling rules specified in Section 5.2.4 will be applied to all IGA related and PASI related analyses.

### **6. USABILITY AND ACCEPTABILITY ASSESSMENTS**

#### **6.1. Definition**

##### **6.1.1. Successful, Problem-Free Injections**

Successful, problem-free self-injection (usability) using the SelfDose device will be assessed by the completion of the Observer Injection Checklist at Week 0. Study-site personnel will observe the subject to confirm successful completion of the 3 steps, as described in the instructions for use, required to effectively and safely use the device to deliver the correct dose: (1) remove the cap, (2) position device on the injection site, and (3) inject complete dose. A successful, problem-free self-injection is defined as below:

Observer Injection Checklist	Required completion for successful, problem-free injection
(1) Remove cap: Did subject successfully remove cap	Yes
(2) Position device on injection site: Did the subject select the correct injection site?	Yes
(2) Position device on injection site: Did the subject position the device at approximately a 90 degree angle on the injection site	Yes
(3) Inject complete dose: Did the subject push the handle all the way down so the orange dose indicator disappeared completely?	Yes
(3) Inject complete dose: Were there any device-related problems associated with this injection?	No

### 6.1.2. Self-Injection Assessment Questionnaire

Subjects will be asked to rate the acceptability of their experience using the SelfDose device with the SIAQ which was developed and validated in patients with rheumatoid arthritis (RA). A paper version of the SIAQ will be used in this study.

The SIAQ includes 6 domains: feelings about injections, self-image, self-confidence, pain and skin reactions during or after the injection, ease of use of the self-injection device, and satisfaction with self-injection. Each domain is derived from one or multiple items. The subject rates each item of the SIAQ on a 5-6 point semantic Likert-type scale.

The PRE-self-injection module of the SIAQ includes items assessing domains of feelings about injections, self-confidence, and satisfaction with self-injection, while the POST-self-injection module of the SIAQ includes items assessing all 6 domains. In this study, the subject will complete the PRE-self-injection module before the first self-injection at Week 0, and will complete the POST-self-injection module after self-injection at Weeks 0, 4, 12, and 28.

#### **Scoring**

Respondent rates items 1-9 of the PRE SIAQ and 15-21 of the POST SIAQ on a 5-point semantic Likert-type scale, and items 10-14 of the POST SIAQ on a 6-point semantic Likert-type scale. For all items, a score of 1 corresponds to the subject's worst experience and a score of 5 or 6 corresponds to the subject's best experience.

The scoring of domains is performed in 2 steps ([Table 3](#)):

- The raw item scores ranging from 1 to 5 (or 1 to 6) are transformed into scores ranging from 0 (worse experience) to 10 (best experience).
- The transformed scores for items contributing to a domain are then averaged into a domain score. Domain scores are calculated only if at least half of the domain items are completed. Domain scores from the PRE module are summarized only with the corresponding domain scores from the POST modules.

Table 3: The calculation of SIAQ scores are as follows:				
	Items	Transformed item score	Domain score calculation	Domain score range
PRE module domain				
Feeling about self-injection	1–3	(raw score-1) x 2.5	Average of transformed item scores	0–10
Self-confidence	4–6	(raw score-1) x 2.5		
Satisfaction with self-injection	7	(raw score-1) x 2.5		
POST module domain				
Feeling about self-injection	1–3	(raw score-1) x 2.5	Average of transformed item scores	0–10
Self-image	4	(raw score-1) x 2.5		
Self-confidence	5–7	(raw score-1) x 2.5		
Pain and reaction during or after the injection	8–9	(raw score-1) x 2.5		
Ease of use of the self-injection device	10–14	(raw score-1) x 2		
Satisfaction with self-injection	15–21	(raw score-1) x 2.5		

## 6.2. Analysis Methods

The analyses of device usability and acceptability assessments will be performed through Week 20 and through Week 28 by treatment group for the safety analysis set.

Other than the data handling rules specified in Section 6.1, the analyses for usability and acceptability will be based on observed data without missing data imputation or other data handling rules.

### 6.2.1. Analyses Related to the Device Usability

- The proportion of subjects with successful, problem-free injections (assessment of usability) at Week 0 will be summarized by treatment group and overall.
- The proportion of subjects who had full delivery of the dose confirmed by inspection of the device at Weeks 4 and 12 will be summarized by treatment group and overall.
- A listing of product quality complaints (PQCs) for Selfdose device will be provided.

### 6.2.2. Analyses Related to Acceptability Assessments

#### 6.2.2.1. Analyses for Self-Injection Assessment Questionnaire

- Self-Injection Assessment Questionnaire (SIAQ) domain scores on the 3 domains with items common to the SIAQ PRE- (Week 0) and POST- (Week 0 and Week 12) self-injection modules will be summarized by treatment group and overall at Week 0 and Week 12.

- Self-Injection Assessment Questionnaire POST-self-injection domain scores and change from baseline scores for each domain will be summarized by treatment group and overall at Weeks 0, 4, 12, and 28.

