## 2.5.2. Baseline

In general, the baseline measurement is defined as the closest measurement taken prior to or at the time of the first study agent administration date unless otherwise specified.

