## 7.2. Clinical Laboratory Tests

All clinical laboratory reports will be displayed for the subjects included in the safety analysis set. The clinical laboratory parameters to be evaluated by the central laboratory include but are not limited to:

- **Hematology:** hemoglobin, hematocrit, lymphocytes, neutrophils, platelets, red blood cell (RBC) count and white blood cell (WBC) count.
- **Chemistry:** albumin, alkaline phosphatase, alanine aminotransferase, aspartate aminotransferase, total carbon dioxide (CO2), total bilirubin, blood urea nitrogen/urea, calcium, chloride, creatinine, glucose, potassium, total protein, sodium.

Box plots of laboratory measurements and change from baseline will be provided for selected laboratory analytes.

Applicable laboratory results will be graded according to National Cancer Institute's Common Terminology Criteria for Adverse Events (NCI-CTCAE version 4.03). The worst NCI-CTCAE will be summarized by treatment group.

For nonfasting glucose, the screening measurement will be used as the baseline measurement. A listing of subjects with 1 or more NCI-CTCAE toxicity grade  $\geq 2$  abnormalities in hematology and clinical chemistry laboratory measurements will be provided.

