## 7.4. Other Safety Parameters

### 7.4.1. Suicidal Ideation and Behavior

The electronic Columbia-Suicide Severity Rating Scale (eC-SSRS) will be used as a screening tool to prospectively evaluate the potential of guselkumab to induce suicidal ideation and

behavior. The eC-SSRS defines five subtypes of suicidal ideation and behavior in addition to self-injurious behavior with no suicidal intent, and is a fully-structured subject self-report questionnaire, including standardized questions, follow-up prompts, error handling routines, and scoring conventions. The Screening version of the eC-SSRS will be conducted at Screening followed by the Since Last Visit version of the eC-SSRS at all other visits through Week 40.

The eC-SSRS will be performed during each evaluation visit according to the assessment schedule. The eC-SSRS will be performed at screening after signing informed consent, after the pre-SIAQ at Week 0, and before study agent administration, and as the first assessment for all post-baseline visits. The baseline is defined as the most severe/maximum eC-SSRS score at screening and Week 0.

In addition, potential suicide related adverse events including suicidal ideation, suicidal behavior excluding completed suicide, and completed suicide will be identified by the investigators and collected in the eCRF.

The following are eC-SSRS categories and have binary responses (yes/no). A “yes” response to any eC-SSRS category will be assigned a score as below:

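### Does the unnamed SIAQ baseline leave the planned change-from-baseline summary undefined?

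*SAP*

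**What the plan says.** SAP Section 6.1.2 describes two SIAQ modules. On the first: "The PRE-self-injection module of the SIAQ includes items assessing domains of feelings about injections, self-confidence, and satisfaction with self-injection". The POST module covers all six domains, adding self-image, pain and skin reactions, and ease of use. PRE is completed before the first self-injection at Week 0; subjects "will complete the POST-self-injection module after self-injection at Weeks 0, 4, 12, and 28".

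Section 6.2.2.1 then has two bullets on the SIAQ. The first summarises domain scores on "the 3 domains with items common to the SIAQ PRE- (Week 0) and POST- (Week 0 and Week 12) self-injection modules". The second takes the POST domain scores and adds that "change from baseline scores for each domain will be summarized by treatment group and overall at Weeks 0, 4, 12, and 28".

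No SIAQ baseline is named in either section. The general rule in Section 2.5.2, introduced as holding in general, takes "the closest measurement taken prior to or at the time of the first study agent administration date unless otherwise specified". The scoring text in Section 6.1.2 also restricts PRE domain scores to summaries alongside their POST counterparts.

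**The concern.** A change score needs a baseline, and the general rule can be read as pointing to PRE. PRE is the last SIAQ measurement before dosing, and Section 7.4.1 confirms the order by placing the Week 0 eC-SSRS "after the pre-SIAQ at Week 0, and before study agent administration". PRE has no score for three of the six POST domains, so a change for each domain could not be produced. For satisfaction, Table 3 uses one PRE item against seven POST items, so that change would not be like-for-like.

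The SAP also shows that it can name a special baseline when it wants one. Section 7.2 says: "For nonfasting glucose, the screening measurement will be used as the baseline measurement". Section 7.4.1 says: "The baseline is defined as the most severe/maximum eC-SSRS score at screening and Week 0". Nothing similar appears for the SIAQ.

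The risk is that two programmers produce different tables under one title. What is at stake is a descriptive acceptability summary under a secondary objective.

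**Working it through.** The SAP gives no figure to reproduce. The check counts the cells of the planned change table under each candidate baseline, then asks which candidate the text supports.

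**Inputs (SAP Section 6.1.2, Table 3; visits from Section 6.2.2.1)**

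| Domain | PRE items | POST items |
|---|---|---|
| Feelings | 3 | 3 |
| Self-image | none | 1 |
| Self-confidence | 3 | 3 |
| Pain and reaction | none | 2 |
| Ease of use | none | 5 |
| Satisfaction | 1 | 7 |

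Visits: Weeks 0, 4, 12 and 28. Cells in the change table: 6 domains × 4 visits = 24.

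**PRE as baseline**
- No baseline (self-image, pain, ease of use): 3 × 4 = 12 cells.
- Satisfaction, one item against seven: 1 × 4 = 4 cells.
- Feelings and self-confidence, equal item counts: 2 × 4 = 8 cells.
- Total: 12 + 4 + 8 = 24.

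**POST Week 0 as baseline**
- Weeks 4, 12 and 28: 6 × 3 = 18 informative cells.
- Week 0: 6 × 1 = 6 cells, zero by construction.
- Total: 18 + 6 = 24.

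**Where the two readings differ after Week 0.** Of the 18 cells at Weeks 4, 12 and 28, 3 × 3 = 9 (the common domains) have a value under both readings. The other 9 have a value only with POST Week 0. In the first nine, for a subject with all scores, the readings differ by

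(POST_t − PRE) − (POST_t − POST_0) = POST_0 − PRE,

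which is the shift across the first self-injection. The documents give no data on its size.

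**Would a reader of the table notice?** Yes, from the Week 0 change column. With POST Week 0 as baseline it is zero (or left blank) for all six domains. With PRE it shows real changes for three domains and nothing for the other three. The two patterns cannot be confused.

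**Which reading does the text support?**
- Section 2.5.2 refers to the date of first administration, not the time. PRE and POST Week 0 both fall on that date, so the rule does not settle the matter.
- The first bullet of Section 6.2.2.1 already handles PRE against POST and stops at the three common domains. The second bullet is about the POST series, whose first value is POST Week 0.
- The request for a change in each domain can be met only by POST Week 0.
- The scoring text keeps PRE scores beside matching POST domains. PRE as baseline for all six is therefore a use that the SAP does not contemplate.

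**A clerical slip nearby.** The scoring text assigns items 1–9 of PRE to the 5-point scale, but Table 3 lists PRE items 1–7 only. Table 3 has POST items 1–9, 10–14 and 15–21 (9 + 5 + 7 = 21), and gives items 1–9 the 5-point transformation, (5 − 1) × 2.5 = 10. The scoring can be taken from Table 3.

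**The case for a change.** The strongest case for a change is that the sentence points both ways. Listing Week 0 among the change visits makes sense only if the baseline precedes POST Week 0, which favours PRE; asking for every domain makes sense only with POST Week 0. In nine cells both readings give a plausible number, and Section 6.2 rules out other data handling rules that might decide between them. One sentence, written before programming, would remove the doubt at almost no cost.

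Part of this stands: the baseline is not named, and the nine cells would differ by POST_0 − PRE. The Week 0 argument is weak, because one visit list serves both scores and changes, and Week 0 is needed for the scores. An empty or zero column at Week 0 is a lesser oddity than three domains with no change at any visit. The fear of an undetected discrepancy does not stand, since the Week 0 column identifies the baseline. The low cost of a sentence is true, but it would only record the choice an analyst would make anyway.

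**Conclusion.** The concern is right that SAP Section 6.2.2.1 names no SIAQ baseline. It does not hold that the general rule selects PRE and so breaks the analysis. The rule is neutral between two measurements on the same date, and POST Week 0 is the only one that serves all six domains: 18 informative cells and 6 trivial zeros, against 12 cells without a value under PRE. The comparison before and after the first injection is kept as side-by-side scores in the first bullet.

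The consequence is confined to observed-data acceptability summaries with no planned test. No co-primary or major secondary analysis, error rate or sample size depends on them. The matter is a gap that analysts fill sensibly, with the baseline named in a table footnote, and the PRE item range is a clerical slip. No change to the plan is called for.

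This rests on two assumptions: that the analyst reads the second bullet as a POST-series summary, and that the Week 0 change column is shown or its omission explained. The item wording is not in the SAP, so equal item counts in feelings and self-confidence do not prove that the items are the same; the conclusion does not depend on it.

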#### 6.2.2.2. Analyses for SelfDose Subject Questionnaire

- Ratings for the SelfDose Subject Questionnaire will be summarized at Week 12 by question, by treatment group and overall.

### 7. SAFETY

Safety will be assessed by summarizing the incidence and type of AEs and examining changes in laboratory parameters (hematology and chemistry), vital signs, and suicidal ideation and behavior.

In all the safety analysis, subjects who were randomized and received at least 1 (partial or complete) dose of study agent administration will be included and analyzed according to the treatment they actually received, regardless of the treatment assigned at randomization. No formal statistical comparison is planned.

Depending on the safety data categories, the cumulative safety data will be analyzed through different study periods which include but are not limited to through Week 16 and through the whole study period as appropriate. Unless otherwise specified, tabular summaries of safety events for key study periods are in general presented as follows:

#### **Summaries through Week 16 (placebo-controlled period):**

Safety data through Week 16 will be summarized by treatment groups:

- Placebo
- Guselkumab

This allows between-group comparisons of safety between the guselkumab group and the placebo group based on similar follow-up period in each group.

#### **Summaries through Week 20 or through Week 40**

Safety data through Week 20 and through Week 40 will be summarized by treatment group defined as follows:

1. **Placebo → Guselkumab 100 mg:** all subjects who were randomized to placebo at Week 0, started treatment with placebo only, and later crossed over to receive treatment with guselkumab. Only the safety events/measurements from these subjects that occurred on or after their first administration of guselkumab 100 mg will be included in this group.
2. **Guselkumab 100 mg:** all subjects who were randomized to guselkumab 100 mg at Week 0 and received study agent with guselkumab 100 mg. All the safety events/measurements from these subjects that occurred beginning at Week 0 will be included in this group.

3. **Combined Guselkumab 100 mg:** all subjects as described above in the Placebo → Guselkumab 100 mg and the Guselkumab 100 mg groups.

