### 1.2. Trial Design

This is a Phase 3, randomized, double-blind, multicenter, placebo-controlled study evaluating the efficacy, safety, PK, immunogenicity, usability, and acceptability of guselkumab delivered using the SelfDose device in subjects with moderate to severe plaque-type psoriasis. The target population is adult men or women, with a diagnosis of plaque-type psoriasis (with or without PsA) for at least 6 months before the first administration of study drug. Subjects must have moderate to severe plaque-type psoriasis defined by PASI  $\geq 12$ , IGA  $\geq 3$ , and involved body surface area (BSA)  $\geq 10\%$ . Subjects must be candidates for either systemic therapy or phototherapy for psoriasis, and may have previously received some systemic therapies (Protocol Inclusion Criteria, Exclusion Criteria) or phototherapy for psoriasis. Subjects with nonplaque forms of psoriasis (eg, erythrodermic, guttate, or pustular) or with drug-induced psoriasis (eg, a new onset of psoriasis or an exacerbation of psoriasis from beta blockers, calcium channel blockers, or lithium) are excluded. Subjects who have ever received guselkumab are also excluded.

Approximately 75 subjects who satisfy all inclusion and exclusion criteria will be randomized in a 4:1 ratio to 1 of 2 arms:

[figure not shown]
- **Group I** (n=60): guselkumab 100 mg at Weeks 0, 4, 12, 20, and 28; placebo at Week 16 to maintain the study blind.
- **Group II** (n=15): placebo at Weeks 0, 4, and 12; cross over to guselkumab 100 mg at Weeks 16, 20, and 28.

Week 28 is the last dosing visit; subjects will be followed for an additional 12 weeks and have a final safety visit at Week 40. The end of the study is defined as the time when last subject completes the Week 40 visit.

There are 2 database locks (DBLs) in this study, 1 at Week 20, and 1 at Week 40.

A diagram of the study design is provided below.

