### 7.1. Adverse Events

The verbatim terms used in the CRF by investigators to identify adverse events will be coded using the Medical Dictionary for Regulatory Activities (MedDRA). Any AE occurring at or after the initial administration of study agent through the end of the trial is considered to be treatment emergent. If the event occurs on the day of the initial administration of study agent, and either event time or time of administration are missing, then the event will be assumed to be treatment emergent. If the event date is recorded as partial or completely missing, then the event will be considered to be treatment emergent unless it is known to be prior to the first administration of study agent based on partial onset date or resolution date. All reported treatment-emergent adverse events will be included in the analysis. For each adverse event, the number and percentage of subjects who experience at least 1 occurrence of the given event will be summarized by treatment group.

Summary tables will be provided for:

- AEs
- Serious AEs (SAEs)
- AEs leading to discontinuation of study agent
- AEs by severity
- AEs by relationship to study agent
- Infections
- Serious infections
- Infections treated with oral or parenteral antimicrobial treatment
- Injection-site reactions
- AEs of psoriasis

In addition to the summary tables, listings will be provided for subjects who:

- Had SAEs
- Had AEs leading to discontinuation of study agent
- AEs of severe intensity
- Serum sickness-like reactions and anaphylactic reactions

In addition, a listing will be provided of all AEs that occurred after Week 16 for subjects who were randomized to placebo at Week 0 and were not crossed over to receive guselkumab.

Any unfavorable or unintended sign that occurs at the injection site is an injection site reaction and will be recorded as an injection site reaction by the investigator on the eCRF. An infection is defined as any AE that was recorded as an infection by the investigator on the eCRF.

The treatment-emergent adverse events of psoriasis include any event of erythrodermic psoriasis, pustular psoriasis, guttate psoriasis, inverse psoriasis, palmo-plantar psoriasis and worsening or exacerbation of psoriasis. Frequency of these events will be summarized.

Since safety should be assessed relative to exposure and follow-up, most AE summary tables will include average weeks of follow-up and average number of study agent administrations for each treatment group.

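### The Week 20 and Week 40 safety tables show only crude AE percentages for guselkumab columns whose follow-up differs by design, so those columns are not directly comparable

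*SAP*

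**What the plan says.** SAP Section 1.2 randomizes about 75 subjects 4:1. Group I (60 subjects) receives "guselkumab 100 mg at Weeks 0, 4, 12, 20, and 28; placebo at Week 16 to maintain the study blind". Group II (15 subjects) receives "placebo at Weeks 0, 4, and 12; cross over to guselkumab 100 mg at Weeks 16, 20, and 28". After the last dose at Week 28, "subjects will be followed for an additional 12 weeks and have a final safety visit at Week 40".

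Section 7, under the summaries through Week 20 or Week 40, defines three columns. The crossover column takes only events on or after the first guselkumab dose. The guselkumab column takes events from Week 0. The combined column is "all subjects as described above in the Placebo → Guselkumab 100 mg and the Guselkumab 100 mg groups".

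Section 7.1 summarizes each AE as the number and percentage of subjects with at least one occurrence. It then states: "Since safety should be assessed relative to exposure and follow-up, most AE summary tables will include average weeks of follow-up", together with the "average number of study agent administrations for each treatment group". Section 7 plans no rate per unit of subject-time.

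Two further statements limit the point. Section 7 plans no formal statistical comparison of safety. The through-Week-16 summaries are the place for comparing guselkumab with placebo, and the SAP justifies this by the similar follow-up in the two groups at that time.

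**The concern.** The percentage of subjects with at least one event generally rises with time observed. Two columns with the same underlying event rate but different follow-up will show different percentages, and a pooled column will show a mixture that depends on how many subjects had short follow-up. Section 7.1 accepts that safety has to be read against exposure and follow-up, and the Week 16 tables are justified on that ground. The Week 20 and Week 40 tables do not meet that condition, because the crossover group starts guselkumab 16 weeks later.

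An average printed beside a percentage warns the reader but leaves the percentage as it is. A combined mean also hides the split behind it. The rate cannot be rebuilt from the table, because time at risk to first event is not shown.

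Safety and tolerability of guselkumab given with the device is a primary objective (Section 1.1), and these are the tables that bring all guselkumab exposure together. The risk is one of reading: the crossover column may look safer than the guselkumab column, or the combined percentage may be taken as a 20-week or 40-week risk.

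**Working it through.** The SAP states no safety figure to reproduce, so the check starts from the design.

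**Inputs from the SAP.** 60 and 15 subjects; guselkumab starts at Week 0 and Week 16; cut-offs at Weeks 20 and 40 (Sections 1.2 and 7).

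**Assumptions.** All 15 placebo subjects cross over, nobody drops out, and risk after the first guselkumab dose is the same in both groups. The SAP gives no AE rate, so the share of subjects affected by 40 weeks on guselkumab is varied from 2% to 70%.

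**Step 1: planned guselkumab follow-up.** For cut-off T, the guselkumab column has T weeks and the crossover column T − 16.
- Week 20: 20 versus 4 weeks, a ratio of 5:1. Combined mean = (60×20 + 15×4)/75 = 16.8 weeks.
- Week 40: 40 versus 24 weeks, a ratio of 1.67:1. Combined mean = (60×40 + 15×24)/75 = 36.8 weeks.

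**Step 2: crude percentages under a constant hazard.** If a proportion p is affected by 40 weeks, the expected proportion after t weeks is 1 − (1 − p)^(t/40). The combined column is (60 × guselkumab + 15 × crossover)/75.

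| Affected by 40 weeks | Table | Guselkumab | Crossover | Combined |
|---|---|---|---|---|
| 20% | Week 20 | 10.6% | 2.2% | 8.9% |
| 20% | Week 40 | 20.0% | 12.5% | 18.5% |
| 50% | Week 20 | 29.3% | 6.7% | 24.8% |
| 50% | Week 40 | 50.0% | 34.0% | 46.8% |

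Worked line (20%, Week 20): 1 − 0.8^0.5 = 0.106; 1 − 0.8^0.1 = 0.022; (60×0.106 + 15×0.022)/75 = 0.089.

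**Step 3: range.** From 2% to 70% affected by 40 weeks, combined divided by guselkumab runs from 0.840 to 0.850 at Week 20 and from 0.920 to 0.947 at Week 40. The relative shortfall is thus 15-16% (0.2 to 6.8 percentage points) and 5-8% (0.2 to 3.7 points). For rare events the ratio tends to 16.8/20 = 0.84 and 36.8/40 = 0.92.

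**Step 4: other hazard shapes.** If all events fall within 4 weeks of the first guselkumab dose, both columns have captured them by either cut-off and the shortfall is about zero. At the other extreme, if events arise only after the crossover group's follow-up has ended, that group adds none and the ratio is 60/75 = 0.80. The shortfall therefore cannot exceed 20% in expectation.

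**Step 5: what a rate would show.** Under a constant hazard, first events per unit of time at risk are equal in all three columns. With 20% affected by 40 weeks the rate is −ln(0.8)/40 × 5200 = 29.0 per 100 subject-years; with 50% it is 90.1. Planned guselkumab follow-up (52-week year) is 60×20/52 + 15×4/52 = 23.1 + 1.2 = 24.2 subject-years through Week 20, after rounding, and 46.2 + 6.9 = 53.1 through Week 40.

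**Step 6: administration counts.** Injections of study agent in Group I number 5 through Week 20 (including the Week 20 dose) and 6 through Week 40; one of them is the Week 16 placebo, leaving 4 and 5 guselkumab doses. Group II has 2 and 3 guselkumab doses. If the Week 16 placebo is counted and Group II's earlier placebo injections are not, the combined averages are (60×5 + 15×2)/75 = 4.4 and (60×6 + 15×3)/75 = 5.4. Counting guselkumab only, they are (60×4 + 15×2)/75 = 3.6 and (60×5 + 15×3)/75 = 4.6. The SAP does not say which count applies.

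**The case against.** The best defence is that the SAP has seen the issue and discloses it. A reader of most AE tables through Week 20 would find about 20, 4 and 16.8 weeks beside the percentages. The placebo comparison is confined to Week 16, where follow-up is similar, and no safety test is planned, so no inferential result is biased. All of this stands, and it makes the point a reporting improvement.

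A reader might go further and infer that the combined column understates guselkumab risk outright. The documents do not support that. The combined percentage is a correct crude incidence over a mean of 16.8 or 36.8 weeks. It is low only if read as a 20-week or 40-week risk, and then by an amount that depends on a hazard the SAP does not give. Only 15 of 75 subjects have the shorter follow-up, and for early-onset events the shortfall vanishes. The SAP defines the column; it does not call it the overall risk estimate.

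A reader might also infer that the average number of administrations is wrong because Group I receives "placebo at Week 16 to maintain the study blind". That is an ambiguity and not a shown error: Section 7.1 does not say which injections count in the guselkumab columns, and no AE percentage uses that average as its denominator.

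Rates have limits of their own. An exact Poisson interval on total events would be too narrow where one subject has repeat events, such as recurrent infections. Subject-years also suit injection-site reactions poorly, since these follow injections. What remains after the defence is that the columns sit side by side on a measure that depends on follow-up, with nothing in the plan that adjusts for it.

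**Conclusion.** The point holds as a matter of reporting. By design, the crossover and guselkumab columns differ in guselkumab follow-up (4 versus 20 weeks, then 24 versus 40 weeks), their crude percentages are not directly comparable, and the printed averages do not make them so. The contrast between these two columns is the larger effect: with 20% of subjects affected by 40 weeks and identical hazards, the Week 20 table would be expected to show 2.2% against 10.6%. The effect on the combined column is modest: a relative shortfall of about 15-16% at Week 20 and 5-8% at Week 40 under a constant hazard, and close to none for events soon after first dose. These sizes rest on assumed AE rates, full crossover and no dropout. The imbalance matters more at Week 20 than in the final Week 40 tables. The Week 16 placebo comparison is untouched.

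**What to change.** For AEs, SAEs and infections in the Week 20 and Week 40 tables, keep the percentages and add, for each column, the number of subjects with a first event per 100 subject-years at risk on guselkumab, with an exact Poisson 95% confidence interval. Time at risk runs from the first guselkumab dose to the first event or the end of follow-up in the table. If rates of total events are also shown, use an interval that allows for repeat events within a subject.

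Report injection-site reactions per injection. In the guselkumab columns, show guselkumab administrations separately from placebo injections, and state in Section 7.1 which injections each average counts. The Week 16 tables need no change.

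The cost is SAP wording and modest programming on dates and doses already collected. The downsides are one more measure per table, a rate that is easy to interpret only if the hazard is roughly constant, and wide intervals in the crossover column at Week 20. With about 1.2 subject-years there (15×4/52 = 1.154), zero events would give an upper limit of −ln(0.025)/1.154 × 100, or about 320 per 100 subject-years. That column should be read as descriptive.
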